6.4 Duration of diabetes

Duration of diabetes will be calculated as:

- Duration of diabetes = (Year of screening visit – Year of Diagnosis) +
(Month of screening visit – Month of Diagnosis) / 12

Note: If the month of diagnosis is unknown, impute “1 (January)” for the calculation. Duration of diabetes will be displayed to one decimal place.

6.5 Medical History and Prior and Concomitant Medications

Medical history will be coded using Medical Dictionary for Regulatory Activities (MedDRA) version 21.0. Prior and Concomitant medications will be coded using the World Health Organisation (WHO) DRUG dictionary version March 2018.

6.6 Extent of Exposure and Compliance to Study Treatment

Study drug exposure during double blind treatment period will be calculated as:

- Exposure duration = (Date of Visit 6 - Date of Randomization Visit)

Note: In case of early withdrawal, the date when unused study treatments are returned will be used to calculate the exposure duration.

Treatment compliance during the double blind treatment period will be calculated as:

- Overall Compliance = 100 X (Number of tablets dispensed – Number of tablets returned)
/ Exposure duration

Note: Overall compliance will be displayed to one decimal place.

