6.4.3 Dosage and Administration of Study Medication

Subjects should understand that they may receive either active treatment or placebo randomly at any time during the study.

Placebo Run-in Period

All subjects will take orally 1 tablet of single-blinded study treatment (placebo), once daily before breakfast during the placebo run-in period. Subjects are not to be informed of the contents of single-blind medication. Placebo run-in period will be 2 weeks for each enrolled subjects.

Double-blind Treatment Period

All subjects randomized will take the first dose of double-blinded study treatment from the randomization visit (Day 1). All subjects will take orally 1 tablet of double-blinded study treatment (20 mg tablet or placebo tablet), once daily before breakfast during the double-blind treatment period. Double-blind treatment period will be 24 weeks for each enrolled subjects.

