- Review use of concomitant treatments
- Blood and urine is to be drawn and sent to the central laboratory according to the local procedure for evaluation of haematology, clinical chemistry, urinalysis, HbA1c, FPG, fasting insulin, C-peptide and glucagon
- Evaluation for any AEs including hypoglycaemic episodes experienced by the subjects since last visit
- Review subject diary
- MP-513 or placebo will be dispensed to the subjects. Unused medication has to be returned to the site
- Subjects are to be instructed that they have to return for the next scheduled visit day.

Treatment Visit 6 (Week 24 plus/minus 7 days of treatment/Early termination visit: date of discontinuation* plus 7 days)

*Date of discontinuation is defined as the date of decision of discontinuation for subjects by the investigator.

This visit is the regular **end of treatment visit**. In case of premature termination, the same evaluations have to be performed as **the early termination visit**.

The following observations/procedures are to be performed and checked:

- Vital signs, body weight and ECG
- Review use of concomitant treatments
- Blood and urine is to be drawn and sent to the central laboratory according to the local procedure for evaluation of haematology, clinical chemistry, urinalysis and HbA1c, FPG, fasting insulin, C-peptide and glucagon.
- A serum pregnancy test is to be performed in females with childbearing potential.
- Evaluation for any AEs including hypoglycaemic episodes experienced by the subjects since last visit
- Review and final collection of subject diary
- Unused MP-513 or placebo has to be returned to the site.

Follow-up Visit (Week 26 plus 14 days following completion / Early termination of double-blind treatment period)

Two weeks after end of treatment, a telephone follow-up visit will take place to ask the subjects about any AEs including hypoglycaemic episodes experienced by the subjects since the last visit and use of concomitant treatments.

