7.8 Use of an “Efficacy Subset” of Subjects

Subjects in Full Analysis Set (FAS) who complied with the protocol (i.e. no major protocol violations), who have completed at least 8 weeks of double blinded medication and who have >75% treatment compliance with the investigational product (MP-513 or placebo) during the Double-blind treatment period will form a Per-Protocol set (PPS). Major protocol deviations will be assigned during Blind Data Review Meeting (BDRM) that will be held before database lock.

Analysis based on PPS will serve as a supportive analysis for primary efficacy endpoint.

The FAS and PPS are defined in [section 8.3](#).

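### SAP 6.6 runs exposure to the tablet-return date for early withdrawals, which overstates exposure, understates compliance when return lags the last dose by two or more days, and can misplace borderline subjects in the PPS

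*SAP*

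**What the plan says.** SAP 6.6 defines "Exposure duration = (Date of Visit 6 - Date of Randomization Visit"), with no day added. For subjects who leave early it substitutes another end date: "In case of early withdrawal, the date when unused study treatments are returned will be used to calculate the exposure duration". Compliance is "Overall Compliance = 100 X (Number of tablets dispensed – Number of tablets returned") divided by that exposure. Protocol 6.4.7 uses the same tablet count over Treatment Visit 6 minus the Randomization Visit.

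In Protocol 6.6.1, Treatment Visit 6 doubles as the early termination visit. It may take place up to 7 days after discontinuation, and unused tablets are handed back there. The anchor for that window is not the last dose: "Date of discontinuation is defined as the date of decision of discontinuation for subjects by the investigator".

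Compliance then decides membership of the PPS. SAP 7.8 and 8.3 and Protocol 6.9.1.3 admit FAS subjects without major violations "who have completed at least 8 weeks of double blinded medication and who have >75% treatment compliance with the investigational product". Neither document says how the 8 weeks are to be counted. SAP 8.6 also tabulates exposure and compliance, including a split at 75%, on the FAS, PPS and safety set.

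**The concern.** The two halves of the compliance ratio stop at different times. The numerator stops growing at the last tablet, while the denominator runs on until the tablets come back. Days off drug after withdrawal are therefore reported as exposure and also scored as missed doses.

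At stake are the exposure and compliance tables and PPS membership. The cut-off is ">75% treatment compliance with the investigational product (MP-513 or placebo) during the Double-blind treatment period", so a subject who took enough tablets while on treatment could fall below it because of a late return visit. The error can also run the other way. If the 8-week criterion is read from SAP exposure, a subject dosed for less than 8 weeks could be counted as having reached it. The PPS analysis is one of only two supportive analyses of the primary endpoint (SAP 8.7.1.2).

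**Working it through.** The documents give no exposure or compliance figure to reproduce, so the check applies the SAP formula directly.

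**Inputs**
- One tablet a day: "All subjects will take orally 1 tablet of double-blinded study treatment (20 mg tablet or placebo tablet), once daily before breakfast" (Protocol 6.4.3).
- First dose on the day of randomization: "All subjects randomized will take the first dose of double-blinded study treatment from the randomization visit (Day 1") (Protocol 6.4.3).
- Exposure is end date minus randomization date, with no +1 (SAP 6.6).
- The return visit is up to 7 days after the decision date (Protocol 6.6.1).
- D = days from first to last dose, inclusive. c = true adherence over those days.
- G = days from last dose to tablet return. **G is an assumption; the documents do not state it.** It is the sum of (decision − last dose) and (return − decision), and only the second part is limited to 7 days.

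**Formulas**
- The last dose falls on randomization + (D−1) and the return on randomization + (D−1+G).
- SAP exposure = D − 1 + G. True exposure = D. Overstatement = G − 1 days.
- SAP compliance = 100 × c × D / (D − 1 + G). The correct value is 100 × c.
- The two agree exactly at G=1. At G=0 the SAP value is slightly high (56/55 = 101.8%). It is low for G of 2 or more.

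**Full adherence (c = 1)**

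| D | G=1 | G=7 | G=14 | G=21 | First G at or below 75% |
|---|---|---|---|---|---|
| 56 | 56/56 = 100.0% | 56/62 = 90.3% | 56/69 = 81.2% | 56/76 = 73.7% | 20 (56/75 = 74.7%) |
| 84 | 100.0% | 84/90 = 93.3% | 84/97 = 86.6% | 84/104 = 80.8% | 29 (84/112 = 75.0%) |
| 140 | 100.0% | 140/146 = 95.9% | 140/153 = 91.5% | 140/160 = 87.5% | 48 (140/187 = 74.9%) |

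At G=7 with D=56, exposure is recorded as 62 days instead of 56, which is 6 days too many.

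**True adherence that must be exceeded to stay in the PPS**, 0.75 × (D − 1 + G) / D:
- G=7: 83.0% (D=56), 80.4% (D=84), 78.2% (D=140).
- G=14: 92.4%, 86.6%, 82.0%.

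Example: with D=56, c=80% and G=7, the SAP gives 0.80 × 56/62 = 72.3%, which fails a criterion that 80.0% would pass.

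**8-week criterion.** With D=50 and G=7, SAP exposure is 50 − 1 + 7 = 56 days. If the criterion is read from that figure, 50 days of dosing count as 8 weeks.

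**Compliance ended at the decision date instead** (D=56, c=80%). If the decision is made the day after the last dose, the result is 0.80 × 56/56 = 80.0%. If it is made on the last-dose day, the result is 0.80 × 56/55 = 81.5%. Both pass, however late the tablets come back.

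**The case against.** The strongest reply is that the rule does little harm in practice and is not the SAP's own invention. Protocol 6.4.7 already divides by the Visit 6 date, and Visit 6 is also the early termination visit, so the SAP note is consistent with the protocol. Nothing in the documents says dosing stops before the return visit. If it continues to the day before, the formula is exact. The only stated window is 7 days, and at that gap a fully adherent subject scores 75% or less only with 18 or fewer doses (18/24 = 75.0%). Such a subject already fails the 8-week requirement. All of this stands, and it limits the size of the point.

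Three stronger readings are tempting, and the documents do not support them:
- **That every early withdrawal gets a wrong value.** Return one day after the last dose gives the right value, and same-day return errs slightly the other way.
- **That fully adherent subjects will drop out of the PPS.** At 56 doses this needs a gap of 20 days or more, which no passage describes.
- **That the error is unbalanced between arms.** Protocol 6.3.3 withdraws subjects for inadequate FPG, so more placebo withdrawals are plausible. But no withdrawal rates are given, and the bias also needs long gaps in those subjects.

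The reply also identifies a real hazard in the obvious remedy. If the last dose closed the compliance denominator for everyone, a subject who stopped tablets after 70 days but attended Week 24 would score 100%. The present rule gives about 42% (70/168). Missed days while still in the study are what a tablet count should detect.

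Consistency with the protocol does not rescue the rule, because it only means that both documents count off-drug days.

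**Conclusion.** The concern holds as a minor definitional error. For early withdrawals the stated rule overstates exposure by G−1 days, and it understates compliance whenever tablets return two or more days after the last dose. At G=7 and 56 dosing days that is 6 days of exposure and a fall from 100% to 90.3%. The realistic PPS losses are subjects with true adherence of about 75–83% (at 56 dosing days), and the band narrows with longer dosing. Wrongful entry to the PPS is possible only if the 8 weeks are taken from SAP exposure, which the documents leave open.

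The result rests on an assumed G. A gap of up to 7 days follows from the visit window if dosing stops at the decision. Longer gaps require dosing to have stopped before it.

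The effect reaches the exposure and compliance summaries and the supportive PPS analysis. The primary FAS analysis is untouched, and SAP 8.8.1 plans no exposure-adjusted event rates.

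**What to change.** - **Exposure, all subjects:** date of last double-blind dose − date of first double-blind dose + 1. Use the tablet-return date only when the last-dose date is missing.
- **Compliance, completers:** keep the Visit 6 denominator, so that stopping tablets while still in the study counts as non-compliance.
- **Compliance, early withdrawals:** end the denominator at the discontinuation (decision) date, not the return date. State how tablets taken after that date are handled, so that numerator and denominator cover the same days.
- **PPS:** say that the 8 weeks are counted from the corrected exposure.
- **Alignment:** amend Protocol 6.4.7 to match, or record the departure in SAP section 5, which currently declares no changes to the planned analysis.

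The cost is a small wording change and reliance on a final-dose date. The 14-day adverse event window (Protocol Table 2, footnote 3) already requires that date. No visit or assessment is added.

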6.7 Efficacy Variables

At each scheduled visit, blood sample will be collected from each subject to evaluate HbA1c, fasting plasma glucose (FPG), fasting insulin, C-peptide and glucagon. Blood sample will be analysed in designated central laboratory. Body weight (Kg) will be measured at each scheduled visit.

HOMA-IR and HOMA-β will be evaluated by FPG and fasting insulin as follows:

- $HOMA-IR = \text{Fasting insulin } (\mu\text{U/mL}) * \text{FPG (mg/dL)} / 405$
- $HOMA-\beta = 360 * \text{Fasting insulin } (\mu\text{U/mL}) / (\text{FPG (mg/dL)} - 63)$

Efficacy variables units for analysis are described in Table 4.

Table 4 Efficacy Variable Units

Variables	Conventional Units	How to Convert	Units for Analysis
HbA1c	%	-	%
FPG	mg/dL	-	mg/dL
Fasting insulin	μU/mL	-	μU/mL
C-peptide	ng/mL	-	ng/mL
Glucagon	pmol/L	Multiply with 0.27241	pg/mL
HOMA-IR	-	-	μU.mg/mL ²
HOMA-β	-	-	-
Body Weight	Kg	-	Kg

The efficacy variables will be evaluated for change from baseline. The change from baseline at post-baseline visits will be computed as:

- $\text{Change from baseline} = \text{Assessed/observed value at post-baseline visit} - \text{Value at baseline visit.}$

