6.6.2.3 Other Efficacy Parameters

Insulin, C-peptide and glucagon will be taken in a fasting state. Blood samples will be collected at the sites and parameters will be measured at a central laboratory.

Homeostatic model assessment (HOMA)

Homeostatic Model Assessment-Insulin Resistance (HOMA-IR) and HOMA- β will be evaluated by fasting glucose and fasting insulin as follows:

$$\text{HOMA-IR} = \text{fasting insulin (mU/L)} * \text{fasting glucose (mg/dL)} / 405$$

$$\text{HOMA-}\beta = 360 * \text{fasting insulin (mU/L)} / (\text{fasting glucose (mg/dL)} - 63)$$

Body weight

Body weight will be measured at the beginning of the respective visits.

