6.8.2 Clinical Laboratory Evaluations

Clinical laboratory parameters to be measured and their units for analysis are shown in the following table.

Table 5 Clinical Laboratory Parameters and Units

Variables		Conventional Units	How to Convert	Units for Analysis
Haematology	Haemoglobin	g/dL	-	g/dL
	Haematocrit	%	-	%
	Red blood cell count	$\times 10^6/\mu\text{L}$	Multiply with 10^2	$\times 10^4/\mu\text{L}$
	White blood cell count	$\times 10^3/\mu\text{L}$	Multiply with 10^2	$\times 10/\mu\text{L}$
	Platelet count	$\times 10^3/\mu\text{L}$	Divide by 10	$\times 10^4/\mu\text{L}$
Blood Chemistry	AST	U/L	-	U/L
	ALT	U/L	-	U/L
	Gamma-glutamyl transferase (GGT)	U/L	-	U/L
	Lactate dehydrogenase (LDH)	U/L	-	U/L
	Alkaline phosphatase	U/L	-	U/L
	Total bilirubin	mg/dL	-	mg/dL
	Total cholesterol	mg/dL	-	mg/dL

Variables	Conventional Units	How to Convert	Units for Analysis	
Blood Chemistry	Triglycerides	mg/dL	-	mg/dL
	Low-density lipoprotein cholesterol (LDL-C)	mg/dL	-	mg/dL
	High-density lipoprotein Cholesterol (HDL-C)	mg/dL	-	mg/dL
	Blood urea nitrogen	mg/dL	-	mg/dL
	Creatinine	mg/dL	-	mg/dL
	Uric acid	mg/dL	-	mg/dL
	Total protein	g/dL	-	g/dL
	Albumin	g/dL	-	g/dL
	Globulin	g/dL	-	g/dL
	Albumin/globulin ratio	-	-	-
	Direct bilirubin	mg/dL	-	mg/dL
	Creatine kinase	U/L	-	U/L
	Sodium	mEq/L	-	mEq/L
	Potassium	mEq/L	-	mEq/L
	Chloride	mEq/L	-	mEq/L
	Calcium	mg/dL	-	mg/dL
Magnesium	mg/dL	-	mg/dL	
Phosphate	mg/dL	-	mg/dL	
Urinalysis	Glucose	-	-	-
	Protein	-	-	-
	Occult blood	-	-	-
	Urobilinogen	-	-	-
	Ketone bodies	-	-	-
	pH	-	-	-

Any value "Lower Limit of Quantification", e.g. "< x.xx" will be analysed as numerical value "x.xx".

Females of childbearing potential will have serum pregnancy test.

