8.7.3 Analysis of Other Efficacy Variables

All other efficacy endpoint will be analysed using FAS. The other efficacy endpoints are as follows:

- Proportion of subjects who achieved HbA1c < 7.0% at Week 24
- Change in fasting insulin, C-peptide, and glucagon from baseline to Week 24
- Change in HOMA-IR and HOMA-β from baseline to Week 24
- Change in body weight from baseline to Week 24
- Change in HbA1c and FPG from baseline to Week 12

Proportion of subjects who achieved HbA1c < 7.0% at Week 24 (LOCF):

For the proportion of subjects who achieved HbA1c < 7.0% at Week 24 (LOCF), the comparison between treatments will be performed using logistic regression with treatment as fixed effect and baseline HbA1c value as a covariate. The subjects who have HbA1c < 7.0% at baseline will be excluded from the analysis.

The odds ratio (OR) with 95% Wald CIs will be presented for between treatment groups comparison of responder rate (i.e. proportion of subjects who achieved HbA1c < 7.0% at Week 24). The Wald Chi-Square p-value for significance of treatment effect after controlling for baseline HbA1c will also be displayed.

For logistic regression analysis, the dichotomous response variable will be coded as '1' (for subjects who achieved HbA1c < 7.0% at Week 24) and '0' for subjects for whom HbA1c ≥ 7.0% at week 24.

The frequency count and percentage of subjects who achieved HbA1c < 7.0% at week 24 will also be summarized by treatment groups.

Other efficacy endpoints:

For the remaining other efficacy endpoints, namely;

- Change in fasting insulin, C-peptide, and glucagon from baseline to Week 24
- Change in HOMA-IR and HOMA-β from baseline to Week 24
- Change in body weight from baseline to Week 24
- Change in HbA1c and FPG from baseline to Week 12

The line graph for mean change in other efficacy endpoints from baseline to Week 24 and Week 24 (LOCF) will be presented. The 95% CIs will also be shown in the graph with error bar. The plots of Week 24 and Week 24 (LOCF) will not be connected.

The same statistical methodology as described for primary analysis on primary efficacy endpoint will be used.

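### SAP Table 4: the glucagon conversion factor of 0.27241 cannot turn pmol/L into pg/mL for a peptide hormone

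*SAP*

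**What the plan says.** SAP section 6.7 makes Table 4 the source for the analysis units: "Efficacy variables units for analysis are described in Table 4". The glucagon row has pmol/L under conventional units, "Multiply with 0.27241" under how to convert, and pg/mL under units for analysis. It is the only row of Table 4 with a conversion.

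The protocol, section 6.6.2.3, says of insulin, C-peptide and glucagon: "Blood samples will be collected at the sites and parameters will be measured at a central laboratory". It gives a unit for insulin in the HOMA formulas but none for glucagon, and no molar mass or other conversion factor appears in either document.

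SAP section 8.7.3 lists "Change in fasting insulin, C-peptide, and glucagon from baseline to Week 24" among the other efficacy endpoints and sets the analysis: "The same statistical methodology as described for primary analysis on primary efficacy endpoint will be used". That means ANCOVA with baseline as covariate and LOCF at Week 24, reported as LS means, treatment difference, SEs and CIs. A line graph (8.7.3) and full subject listings (8.7) are added.

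**The concern.** A conversion from a molar to a mass concentration is fixed by the molar mass. For any substance heavier than 1,000 g/mol, the number in pg/mL must be larger than the number in pmol/L. Table 4 makes it smaller, by a factor of almost four.

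A programmer working from the SAP has only this row to follow. The estimates and confidence intervals for glucagon would then carry a size and a unit that do not match. A reader comparing the result with other glucagon data could be misled by an order of magnitude. The endpoint also bears on mechanism: the protocol's introduction says that DPP-4 inhibitors lower glucagon, so the size of the change is likely to be read and quoted.

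**Working it through.** **Inputs**
- Factor 0.27241, source unit pmol/L, analysis unit pg/mL: SAP Table 4.
- Molar mass M of glucagon: not in the documents. Assumption: about 3,483 g/mol, the sum of the residue masses of a 29-residue chain. Plausible range shown: 3,000 to 4,000 g/mol. The figure of 1,000 g/mol is used only as the floor at which the contradiction begins.

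**Formulas**
- 1 pmol/L = M pg/L = M/1000 pg/mL, so pmol/L to pg/mL needs the factor M/1000.
- In the other direction, pg/mL to pmol/L needs 1000/M.

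**Step 1. The row as printed.** M = 0.27241 × 1000 = 272.4 g/mol. A chain of only five residues of the lightest amino acid (glycine) already weighs 5 × 57.05 + 18.02 = 303 g/mol. The printed factor therefore cannot be reproduced for a peptide hormone, whatever its exact mass.

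**Step 2. Is the column order to blame?** SAP section 6.8.2 introduces Table 5 in the same layout: "Clinical laboratory parameters to be measured and their units for analysis are shown in the following table". Its three conversions work from left to right:
- red cells: 5 × 10^6/µL, times 10^2, gives 500 × 10^4/µL;
- white cells: 6 × 10^3/µL, times 10^2, gives 600 × 10/µL;
- platelets: 250 × 10^3/µL, divided by 10, gives 25 × 10^4/µL.

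All three agree, so the layout does not explain the glucagon row.

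**Step 3. Reading A: the laboratory reports pmol/L and the factor is wrong.** Understatement = (M/1000)/0.27241.

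| M (g/mol) | Correct factor | Understated by |
|---|---|---|
| 1,000 (floor) | 1.000 | 3.7-fold |
| 3,000 | 3.000 | 11.0-fold |
| 3,483 | 3.483 | 12.8-fold |
| 4,000 | 4.000 | 14.7-fold |

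At 3,483 g/mol the reported value is 0.27241/3.483 = 7.8% of the true one. An illustrative change of −2.0 pmol/L would be reported as −2.0 × 0.27241 = −0.54 pg/mL instead of −2.0 × 3.483 = −6.97 pg/mL.

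**Step 4. Reading B: the laboratory reports pg/mL and the two unit entries are swapped.** Here 0.27241 implies M = 1000/0.27241 = 3,671 g/mol, the right order of magnitude.

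| M (g/mol) | Correct factor | 0.27241 relative to it |
|---|---|---|
| 3,000 | 0.33333 | 18% too low |
| 3,483 | 0.28711 | 5.1% too low |
| 4,000 | 0.25000 | 9% too high |

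The main fault would then be the label, with a possible smaller error in the factor.

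**Step 5. A slip of multiply for divide.** This is a form of reading A. Dividing by 0.27241 is multiplying by 1/0.27241 = 3.671. Against 3.483 that is 3.671/3.483 = 1.054, or 5.4% too high under the assumed mass.

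**Step 6. Effect on the test.** The factor multiplies both the change and the baseline covariate. In a simulated ANCOVA with 240 subjects, the p-value was the same (0.9689) at scale factors 1, 0.27241 and 3.483. The treatment estimate and its SE moved in exact proportion to the factor: the SE was 0.462, 0.126 and 1.609.

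**The case against.** The best case for leaving this as a minor matter has three parts.

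First, glucagon is one of several other endpoints, neither primary nor secondary. A constant factor leaves the p-value and the direction of effect alone, loses no data, and can be undone by multiplication at any time. All of this is true, and it limits the weight of the point. It does not remove it, because SAP section 7.1 commits to estimates and 95% confidence intervals as well as tests, and those are what would be wrong.

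Second, the sizes rest on a molar mass that neither document gives. That also stands: 12.8-fold, 5.1% and 5.4% are conditional figures. The inconsistency itself needs only that glucagon, as a peptide hormone, is heavier than 1,000 g/mol.

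Third, the laboratory may have supplied 0.27241 for its own assay, or the table and listing shells named in the SAP's contents (sections 12 and 13), which are not in the text examined, may state the unit. Either could settle which entry is wrong. Neither would make the row correct as printed.

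**Conclusion.** The row is wrong as written: its two units and its factor are mutually inconsistent. That conclusion is firm and does not depend on an exact molar mass. What remains open is which entry is at fault. The size follows from that: an understatement of about an order of magnitude under reading A, or a wrong label with a factor that may be off by some percent under reading B. Both sizes rest on the assumed molar mass.

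The damage is confined to the glucagon summaries, LS means, differences, SEs, CIs, graph and listing. HbA1c and FPG do not use glucagon, and the HOMA indices use only FPG and insulin. The row should be corrected before the analysis is programmed, but it does not threaten the trial's main conclusions.

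**What to change.** Ask the central laboratory which unit it reports for glucagon and, if a conversion is needed, which factor it confirms. Then correct the row in one of three ways:

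1. Analyse in the reported unit and delete the conversion.
2. If the laboratory reports pmol/L and pg/mL is wanted, keep the units and replace the factor with M/1000.
3. If the laboratory reports pg/mL and pmol/L is wanted, swap the two unit entries and use 1000/M.

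The present factor should not be inverted or kept under swapped labels without that confirmation, since either route may leave an error of about 5% if the molar mass is near 3,483 g/mol. Check that the units in the table, figure and listing shells follow the corrected row.

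The cost is one query, one row of the SAP and one line of derivation code. Nothing changes for patients, samples or data collection.
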